#### 7.7. **Rescue Therapy**

Cold compress should first be used in the management of allergic symptoms. Subjects may be prescribed anti-inflammatory or anti-allergy medication at the Investigator's discretion. If prescribed such anti-inflammatory or anti-allergy medication, the insert will not be removed and subjects will be followed for safety only.

Currently marketed over-the-counter anti-allergy eye drops (i.e., anti-histamine/ vasoconstrictor combination products such as Visine®-A®) may be administered to subjects at the end of the subject's last visit, after all evaluations are completed.

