## **10.7.** General Imputation Methods

Missing data for the primary efficacy variable will be imputed using Markov Chain Monte Carlo (MCMC) multiple imputation techniques on the ITT population, producing twenty "complete" (imputed) datasets which will then be analyzed separately. Results from the separate analyses on the twenty "complete" datasets will be combined for presentation through the use of SAS PROC

CLN-Protocol-0052 Page **41** of **61** 

MIANALYZE. A separate imputation model will be fit for each time point. The model will include variables for treatment, baseline measure, and response measure.

For sensitivity analysis, the ITT population will also be analyzed using the following:

- Observed data only
- Last observation carried forward (LOCF)
- Worst case observation (WCO)
- Baseline observation carried forward (BOCF)

For the LOCF imputation, only post-challenge observations within the same visit will be carried forward. Therefore, there must be post-challenge values available at post-baseline visits to implement LOCF, as pre-challenge values will not be carried forward to post-challenge values and the prior visit values will not be carried forward to the following visit values. Missing values post-challenge will be carried forward from the last observed time point within the same visit, i.e., a missing 5-minute observation at Visit 5b will be imputed from the 3-minute observation from Visit 5b, etc.

For the WCO imputation, missing data due to a subject being prescribed anti-inflammatory or antiallergy medication will be imputed using the worst possible outcome (maximum observed value) from the subject's treatment group, starting at the first time point at which a subject takes an antiinflammatory or anti-allergy medication.

For the BOCF imputation, missing data post-baseline will be imputed with the corresponding time point baseline data from Visit 4a.

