8.5 Adjustments for Multiplicity

All six sets of hypotheses described in Section 2.5 will be tested in a hierarchical order, testing the primary hypotheses first (corresponding to Visit 6b), and then proceeding with the key secondary efficacy hypotheses in the order presented below.

- 1. Visit 6b
- 2. Visit 6a
- 3. Visit 5
- 4. Visit 8b
- 5. Visit 8a
- 6. Visit 7

If at any point in the hierarchical order, statistical significance is not demonstrated, testing will stop, and the remaining tests will be deemed not statistically significant.

There will be no adjustment necessary for testing multiple time points within a visit, as statistical significance at all three post-CAC time points is required for a visit to be deemed statistically significant.

9. Disposition of Subjects

Analysis populations, study completion, and withdrawal from the study will be summarized for the ITT population. The summary table will include the numbers of subjects randomized and included in the analysis populations by randomized treatment group for the ITT population and by actual treatment group for the PP and Safety populations. The summary table will also include the numbers of subjects who completed the study. The reasons for withdrawal will be summarized for the applicable subjects. Reasons for withdrawal will include AE, protocol deviation, lost to follow-up, consent withdrawn, Sponsor termination of study, Investigator decision, unsuccessful insertion, other.

Disposition data for all subjects in the ITT population will be presented in a listing. Protocol deviations for the ITT population will also be presented in a listing.

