12.1 Primary Analysis

The primary efficacy variable is ocular itching evaluated by the subject at $3(\pm 1)$, $5(\pm 1)$, and $7(\pm 1)$ minutes post-CAC at Visit 6b (Day 8; 8 hours from Visit 6a). Ocular itching will be evaluated using the following Ora CalibraTM CAC Ocular Itching Scale as defined in Appendix A.

The average of each subject's eyes' itching score at each post-CAC time point will be used as the unit of analysis for ocular itching.

The primary analysis of ocular itching will be performed on the ITT population with MCMC multiple imputation methodology for missing data using an ANCOVA model for each post-CAC time point at Visit 6b, with the time appropriate post-CAC itching scores at Visit 4a as a covariate and treatment group as the sole factor.

For multiple imputations using MCMC, twenty "complete" (imputed) datasets will be produced and analyzed. Results from the analyses on the twenty "complete" datasets will be combined for presentation using SAS PROC MIANALYZE.

A separate imputation model will be fit for each visit and time point. The imputation model will include variables for treatment, baseline measure (the time appropriate post-CAC scores at Visit 4a), and response measure.

The following SAS code will be used to produce twenty "complete" datasets:

```
PROC MI DATA = INDATA SEED = 59411 NIMPUTE = 20 OUT =
OUTDATA1 MINIMUM=. 0 0 MAXIMUM=. 4 4 ROUND =. 0.25 0.25;
BY VISIT TIME;
MCMC INITIAL = EM;
VAR TREATMENT BASELINE SCORE;
RUN;
```

where

- INDATA is the name of the input dataset;
- OUTDATA1 is the name of the output dataset;
- TREATMENT is the name of the treatment group variable in numeric format;
- BASELINE is the time appropriate post-CAC scores at Visit 4a; and
- SCORE is the average (of right eye [OD] and left eye [OS] for each subject) ocular itching score.

After obtaining twenty "complete" datasets, the following SAS code will be employed to run the analysis of covariance (ANCOVA) models by time point on each dataset:

```
ODS OUTPUT SOLUTIONF = MIXPARMS LSMEANS = LS DIFFS = DIFF;
PROC MIXED DATA = OUTDATA1;
BY VISIT TIME _IMPUTATION_;
CLASS TREATMENT;
MODEL SCORE = BASELINE TREATMENT / SOLUTION;
LSMEANS TREATMENT / PDIFF CL;
RUN;
```

where

- *SUBJID* is the subject ID number;

- BASELINE is the time appropriate post-CAC scores at Visit 4a;
- VISIT is the visit; and
- *TIME* is the time point.

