12.2 Secondary Analyses

12.2.1 Key Secondary Analyses

The key secondary efficacy variables include ocular itching at $3(\pm 1)$, $5(\pm 1)$, and $7(\pm 1)$ minutes post-CAC at visits 5 (Day 7), 6a (Day 8), 7 (Day 14), 8a (Day 15), and 8b (Day 15; 8 hours from Visit 8a).

Ocular itching scores for these time points and visits will be analyzed in a manner similar to the primary analyses using the same analysis populations and imputation methodologies for missing data. All ocular itching scores (including both key secondary and other secondary timepoints) will be included in the listing for primary efficacy ocular itching scores.

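### The multiple imputation at each visit ignores the subject's own earlier post-insertion itching, so it adds nothing to a complete-case ANCOVA and can bias the Day 14–15 comparisons if recorded itching drives missingness

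*SAP*

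**What the plan says.** SAP 12.1 makes multiple imputation by MCMC on the ITT population the primary method. It states: "A separate imputation model will be fit for each visit and time point". On content it states: "The imputation model will include variables for treatment, baseline measure (the time appropriate post-CAC scores at Visit 4a), and response measure". The PROC MI step agrees: it runs by visit and time with "VAR TREATMENT BASELINE SCORE". Protocol 10.7 names the same three variables: "The model will include variables for treatment, baseline measure, and response measure". The analysis model fitted to each imputed dataset is "MODEL SCORE = BASELINE TREATMENT / SOLUTION".

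SAP 12.2.1 analyses itching at Visits 5, 6a, 7, 8a and 8b in the same way, "using the same analysis populations and imputation methodologies for missing data". Those visits follow Visit 6b in the fixed sequence of SAP 8.5, with 8b, 8a and 7 as steps 4, 5 and 6. Protocol 10.9 has secondary endpoints analysed on observed data only, but SAP section 1 says its methods supersede the protocol's, so the imputation governs.

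**The concern.** A subject who misses the Day 14–15 challenges may well have itching scores from Visits 5, 6a and 6b. A subject missing only Visit 6b may have Visits 5 and 6a. None of these scores can enter the imputation, which is therefore valid only if missingness is random given arm and the Visit 4a score.

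The protocol contains routes by which that could fail. Under 7.7, once a subject is prescribed anti-inflammatory or anti-allergy medication, "the insert will not be removed and subjects will be followed for safety only". Under 7.8, a subject whose insert is removed for discomfort or an undesirable reaction is exited, and a subject found with only one insert has no further challenge. The first route, and perhaps the second, could follow itching already recorded on treatment.

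At stake are the size of the estimated Day 14–15 difference and the power of steps 4–6. There is also a point of interpretation. Because the imputation and the ANCOVA share the same predictors, the imputed and observed-data ITT results should nearly coincide by construction, so their agreement would not be evidence of robustness.

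**Working it through.** **1. The plan's own power figure (SAP section 5).** Inputs: 40 per arm, SD 1.0, differences 0.87, 1.08 and 1.13, two-sided 0.05. The standard error is √(2/40) = 0.2236, giving noncentrality 3.89, 4.83 and 5.05 on 78 df. The noncentral t gives 97.0%, 99.8% and 99.9%, with product 96.7%. The stated figures reproduce. They assume complete data, so this point does not change them.

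**2. Precision when missingness is unrelated to itching.** Let m be the fraction missing and r the correlation of the earlier with the later score given baseline. Relative to complete data, the large-sample variance of the difference is:

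- planned model: 1/(1−m)
- with the earlier score: 1 + [m/(1−m)](1−r²)

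The ratios of standard errors, planned over enriched, are:

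- m = 0.05, r = 0.5: √(1.0526/1.0395) = 1.006
- m = 0.20, r = 0.7: √(1.25/1.1275) = 1.053
- m = 0.20, r = 0.85: √(1.25/1.0694) = 1.081

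So the planned standard error is about 1% to 8% larger than necessary.

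**3. Bias when recorded itching drives missingness.** From the documents: 40 per arm, SD 1.0, and an early difference of 1.08 (the 5-minute Visit 6b assumption). Assumed, because the documents give no value: a true Day 15 difference of −0.60, baseline correlation 0.3, r from 0.5 to 0.8, 10% or 20% missing overall, and one missingness mechanism common to both arms with logit slope 0, 1 or 2 per unit of early itching. Each case used 20 imputations, Rubin's rules and 800 replicates (Monte Carlo error of a mean about 0.23/√800 = 0.008). The SAP's minimum, maximum and rounding options were left out. Results for r = 0.7:

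| Missing | Slope | Missing OTX-DP / PV | Planned: estimate (bias) | With earlier score | Power, planned / with |
|---|---|---|---|---|---|
| 10% | 0 | 10.0% / 10.0% | −0.587 (+0.013) | −0.587 | 72.8% / 76.5% |
| 10% | 1 | 5.8% / 14.2% | −0.558 (+0.042) | −0.603 | 65.9% / 73.9% |
| 10% | 2 | 3.8% / 16.2% | −0.505 (+0.095) | −0.608 | 62.0% / 77.0% |
| 20% | 0 | 20.0% / 20.0% | −0.598 (+0.002) | −0.602 | 68.9% / 74.1% |
| 20% | 1 | 12.8% / 27.2% | −0.532 (+0.068) | −0.610 | 58.1% / 74.6% |
| 20% | 2 | 9.4% / 30.5% | −0.441 (+0.159) | −0.607 | 45.8% / 73.4% |

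The +0.013 at slope 0 is noise: the full-data mean in those replicates was −0.588. Complete-case ANCOVA matched the planned imputation to within about 0.001 (for example −0.505 against −0.505).

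Across r = 0.5 to 0.8 and slopes 1 and 2, the bias was 0.037 to 0.116 at 10% missing and 0.050 to 0.184 at 20%. With the earlier score it stayed within about 0.01 of zero. A large-sample check of the same set-up (one million per arm) extends the ends of the range. It gave 0.024 to 0.026 at 5% missing, r = 0.7, slope 1, and 0.19 to 0.20 at 20% missing, r = 0.85, slope 2. In each pair the two values take r as partial or as marginal.

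**4. False positives (r = 0.7, slope 2).** With an early difference of 1.08 but no Day 15 difference, the planned model shifted by +0.091 (10% missing) and +0.161 (20%), against the drug. Two-sided rejection was 7.2% and 10.9%, compared with 5.2% and 4.9% when the earlier score was included. With no early difference and the same mechanism in both arms, the shift was +0.010 and rejection 5.6%.

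**5. Visit 6b.** As an illustration, a shift of 0.08 on the smallest planned effect leaves 0.87 − 0.08 = 0.79. Then 0.79/0.2236 = 3.53, and 3.53 − 1.99 = 1.54, which is about 94% power with 40 observed per arm, against 97.0% as planned.

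**The case against.** Several stronger readings are tempting, and the documents do not support them.

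- *Gaps are filled from baseline alone.* Treatment arm is also in the model. The accurate statement is that Visit 4a is the only itching score of the subject's own that it uses.
- *The Day 14–15 tests are biased.* That is conditional. There is no bias if missingness is unrelated to itching, or if the arms share both early itching and mechanism. Loss of an insert is a separate route to missing challenges, and no passage ties it to itching.
- *The bias could equally favour the drug.* With an effective drug the itchier PV subjects go missing more, which pulls the difference toward zero. A simulation with 45 per arm, effect −1.0 and 19% against 7% missing gives 0.05 to 0.08 units in whichever direction the imbalance is set. But 19% missing on OTX-DP with 7% on PV would need OTX-DP subjects at the same itching to have roughly 10 to 38 times the odds of going missing (slopes 1 and 2). Nothing in the documents suggests that.
- *A false efficacy claim becomes more likely.* The excess two-sided rejections in step 4 fall on the unfavourable side. False positives favouring the drug were 0.3% to 1.3% over 10–20% missing and slopes 1–2, below the nominal 2.5%.
- *The primary conclusion is at risk.* Given the planned effects and power at Visit 6b, it is little affected.

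It is also fair to say that the SAP plans LOCF, BOCF, WCO and observed-data analyses, and that WCO targets rescue directly. These do probe dependence on the imputation. However, LOCF stays within a visit, BOCF uses Visit 4a, WCO uses the arm's worst value, and the repeated-measures model runs visit by visit on data from the same imputation. None uses an earlier on-treatment visit, so the gap stands.

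**Conclusion.** The concern holds in conditional form. The planned imputation carries no information beyond a complete-case ANCOVA. If recorded itching drives missed challenges, and early itching or missingness differs by arm, the Visit 8b, 8a and 7 differences are most plausibly shrunk toward no effect. The shrinkage is about 0.03 to 0.16 units for r = 0.7 over 5–20% missing and slopes 1–2, and about 0.2 in the harshest corner at r = 0.85. The 46% against 73% power contrast is the worst case at r = 0.7 and depends on the assumed Day 15 difference of 0.60.

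If missingness is unrelated to itching, the only cost is 1–8% in the standard error. The missingness rates, slopes, correlations and Day 15 effect are all assumptions. Adding earlier scores deals with missingness explained by recorded itching; it does not deal with missingness that depends on itching never recorded. This is a low-cost improvement aimed mainly at steps 4–6, not a threat to the primary result.

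**What to change.** Restructure the PROC MI input to one row per subject and minute, with each visit's score in its own column. For each target visit, add the same-minute itching scores from all earlier post-insertion visits to the variable list:

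- Visit 6a: Visit 5
- Visit 6b: Visits 5 and 6a
- Visit 7: Visits 5, 6a and 6b
- Visit 8a: Visits 5, 6a, 6b and 7
- Visit 8b: Visits 5, 6a, 6b, 7 and 8a

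Extend the MINIMUM, MAXIMUM and ROUND lists to match, since each needs one entry per variable. Replace the sentence in SAP 12.1 that lists the model's contents, and record the difference from Protocol 10.7 in SAP section 15. Leave the ANCOVA and the testing order as they are. The largest model, for Visit 8b, has eight variables. All the scores are already collected, so the cost is a few lines of code and SAP wording, to be settled before unmasking.

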4.2 Masking and Unmasking

In the case of a medical emergency or occurrence of a serious adverse event (SAE), the randomization code may be unmasked and made available to the Investigator, Sponsor, and/or other study personnel involved in the conduct of the study. In the absence of medical need, the randomization code will not be available to the above individuals until after the study is completed and the database is locked.

In the event of a medical need, the Investigator will treat each subject, as medically required. If the Investigator feels it is necessary to unmask a subject's treatment assignment after an emergency situation, the Investigator may call the Medical Monitor and notify the Sponsor. The treatment assignment will be revealed on a subject-by-subject basis with the approval of the Medical Monitor and Sponsor, leaving the masking of the remaining subjects intact.

The site will receive one emergency unmasking envelope for every product received and the envelopes should be stored in a secured location. The envelopes and product will both be labeled with the same randomization number. The envelopes are sealed and contain the unmasked treatment information for the corresponding study product.

Ocular Therapeutix will make the final determination if the unmasking request will be granted. Once the unmasking request is granted the Investigator or designee should identify and retrieve the emergency unmasking envelope for the given subject. The emergency unmasking envelope should be opened by the designated site personnel. The Investigator must also indicate in source documents and in the electronic case report form (eCRF) that the mask was broken and provide the date, time, and reason for breaking the mask. Any AE or SAE associated with breaking the mask must be recorded and reported as specified in this protocol.

Subjects will have the investigational product (IP) removed immediately if treatment assignment is unmasked.

5. Sample Size and Power Considerations

Approximately 80 subjects will be randomized at Visit 4b in a 1:1 ratio across the two treatment arms (40 OTX-DP; 40 PV). Up to approximately 10 additional subjects may be enrolled to make up for any subjects who did not complete Visit 6b CAC procedures.

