A total of 40 subjects in each treatment arm will provide 97.0%, 99.8%, and 99.9% power to demonstrate a statistically significant difference in ocular itching between OTX-DP and PV treated subjects at each of the 3-, 5-, and 7-minute post-CAC time points of Visit 6b, respectively, assuming a treatment difference of 0.87 units at 3 minutes post-CAC, 1.08 units at 5 minutes post-CAC, and 1.13 units at 7 minutes post-CAC; a standard deviation of 1.0 unit at all time points; and a two-sided Type I error of 0.05.

Assuming independence between time points, 40 subjects per group will have at least 96.7% power to demonstrate a statistically significant difference over all three primary post-CAC time points at Visit 6b for ocular itching between OTX-DP and PV treated subjects.

6. Data Preparation

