8.4 Data Analysis Conventions

Final data analysis will be performed by SDC after the study is completed and the database has been locked and released for unmasking. Statistical programming and analyses will be performed using SAS[®] version 9.4 or higher. Output will be provided in rich text format (RTF) for tables and portable document format (PDF) for tables, listings, and figures using landscape orientation. All study data will be listed by subject, treatment, and visit (as applicable) based on all randomized subjects unless otherwise specified.

Summaries for continuous and ordinal variables will include the number of observations (n), arithmetic mean, standard deviation (SD), median, minimum, and maximum. Minima and maxima will be reported with the same precision as the raw values; means and medians will be presented to one additional decimal place than reported in the raw values. Standard deviations will be presented to two additional decimal places than reported in the raw values. Summaries for discrete variables will include counts and percentages. All percentages will be rounded to one decimal place (i.e., XX.X%). Differences between active treatment groups and placebo will be calculated as active minus placebo and change from baseline will be calculated as follow-up visit minus baseline.

All statistical tests will be two-sided with a significance level of 0.05 (α = 0.05) unless otherwise specified. Confidence intervals (CIs) for differences between treatment groups will be two-sided at 95% confidence. All p-values will be rounded to 4 decimal places; p-values less than 0.0001 will be presented as "<0.0001"; p-values greater than 0.9999 will be presented as ">0.9999."

Unless otherwise specified, summaries will be presented by treatment group and, where appropriate, visit. Listings will be sorted by treatment group, subject number, visit/time point, and parameter as applicable.

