The following SAS code will then be used to combine results across imputations for the treatment means and differences respectively:

```
ODS OUTPUT PARAMETERESTIMATES = PE1;
PROC MIANALYZE DATA = LS;
BY VISIT TIME TREATMENT;
MODELEFFECTS ESTIMATE;
STDERR STDERR;
RUN;
ODS OUTPUT PARAMETERESTIMATES = PE2;
PROC MIANALYZE DATA = DIFF;
BY VISIT TIME TREATMENT;
MODELEFFECTS ESTIMATE;
STDERR STDERR;
RUN;
```

where the statement WHERE _TREATMENT=2 identifies the differences for active minus vehicle. The detailed code will be determined based on the final data.

Least squares means (LS Means) for each treatment, LS Means treatment differences and corresponding 95% CIs as estimated by the ANCOVA model will be provided.

In addition, ANCOVA models accounting for repeated measures will be run at Visit 6b as another supportive analysis. This ANCOVA model will include the time appropriate post-CAC itching scores at Visit 4a as a covariate and treatment group and time point as factors. The LS Means for each treatment, the LS Means treatment difference between OTX-DP and PV, and the corresponding 95% CIs will be calculated from these ANCOVA models. SAS pseudo-code for the ANCOVA model accounting for repeated measures at Visit 6 for multiply imputed data follows (Note: the same imputation routine described above [PROC MI \rightarrow PROC MIXED \rightarrow PROC MIANALYZE] will be employed using the below PROC MIXED pseudo-code):

```
PROC MIXED DATA=INDATA;
BY VISIT _IMPUTATION_;
CLASS SUBJID TREATMENT TIME;
MODEL SCORE = TREATMENT TIME BASELINE;
REPEATED TIME / SUBJECT=SUBJID TYPE=UN;
LSMEANS TREATMENT / PDIFF CL;
RUN;
```

where *INDATA* is the name of the input dataset sorted by *VISIT*, *_IMPUTATION_*, *SUBJID* and *TIME*.

An unstructured variance-covariance matrix will be used for the above repeated measures model. If the model does not converge using the unstructured matrix, the first order autoregressive structure and the compound symmetry structure will be employed, in that order.

Two-sample *t*-tests will also be used as unadjusted sensitivity analyses at each post-CAC time point, as well as non-parametric Wilcoxon rank sum tests for comparing OTX-DP and PV. Mean treatment differences, 95% CIs for each of the means, and 95% CIs for the mean differences will be presented for each post-CAC time point.

The following SAS code will be used for the t-test:

```
PROC TTEST DATA=INDATA;
BY VISIT TIME _IMPUTATION_;
CLASS TREATMENT;
VAR SCORE;

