ODS OUTPUT STATISTICS = OUTPUTDF;
RUN;
PROC MIANALYZE DATA = OUTPUTDF;
BY VISIT TIME CLASS;
MODELEFFECTS MEAN;
STDERR STDERR;
RUN;
```

The following SAS code will be used for the Wilcoxon rank sum test:

```
ODS OUTPUT WILCOXONSCORES = WILCOXON (WHERE=(CLASS=:"1"));
PROC NPAR1WAY DATA = INDATA WILCOXON;
    BY VISIT TIME IMPUTATION ;
    CLASS TREATMENT;
    VAR SCORE;
RUN;
DATA WILCOXON;
  SET WILCOXON;
  BY VISIT TIME;
  MEAN = (SUMOFSCORES - EXPECTEDSUM) /N;
  STDERR = STDDEVOFSUM/N;
RUN;
PROC MIANALYZE DATA = WILCOXON ALPHA = 0.05;
BY VISIT TIME;
MODELEFFECTS MEAN;
STDERR STDERR;
RUN;
```

The ordering of the above code should be adjusted accordingly for the real data, to make sure the tests are performed to compare the treatment group vs. the placebo group.

Sensitivity or supportive analyses will be performed on the ITT population using LOCF, BOCF, and WCO imputations as well as observed data only (see Section 8.2.1 for additional data imputation details). The primary analysis will also be repeated on the PP population with observed data only.

A line graph will be produced to show mean (+/- standard error [SE]) ocular itching score by treatment group (OTX-DP, PV), visit (Visit 6b, Visit 8b), and time point (3, 5, and 7 minutes post-CAC). Mean change from baseline (+/- SE) for each treatment arm will be presented in a similar figure. Both figures will be presented separately for the ITT population using observed data only.

A listing of ocular itching scores for all subjects will also be provided.

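### The pooling code for the primary ANCOVA gives no error degrees of freedom (EDF=), so p-values are slightly too small and 95% CIs about 1.6 to 2.0% too narrow

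*SAP*

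**What the plan says.** SAP Section 12.1 fits an ANCOVA with baseline and treatment to each of 20 imputed datasets. It then combines the LS means in one PROC MIANALYZE call and the differences in another, "PROC MIANALYZE DATA = DIFF". Both calls name only the estimate and its standard error. The section says that "LS Means treatment differences and corresponding 95% CIs as estimated by the ANCOVA model will be provided", and adds that detailed code will be settled once the final data are available.

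Section 8.4 sets the standard: "All statistical tests will be two-sided with a significance level of 0.05". Section 12.2.1 has the key secondary visits "analyzed in a manner similar to the primary analyses using the same analysis populations and imputation methodologies for missing data". The repeated-measures model in Section 12.1 follows the same impute, fit and pool sequence, and the t-test sensitivity analysis is pooled by "PROC MIANALYZE DATA = OUTPUTDF", again without a df option. Neither the SAP nor the protocol states a complete-data df or a small-sample df rule for pooled results.

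**The concern.** A procedure that receives only estimates and standard errors cannot know the sample size. If the user supplies no complete-data df, PROC MIANALYZE uses Rubin's df, which assumes an infinite number and depends only on the number of imputations and the share of variance due to missing data. With 20 imputations and modest missingness that runs to hundreds or thousands, more than the same ANCOVA would have with nothing missing. Imputation would then appear to add information.

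The error is in one direction only: p-values too small and intervals too narrow on the confirmatory test. It can also make planned tables disagree. With little missing data, a t statistic of 1.975 gives p = 0.048 in the pooled primary table but p = 0.052 in the observed-data ANCOVA (Table 14.2.1.6), purely because of the df convention.

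**Working it through.** **Inputs.** From the documents: "Approximately 80 subjects will be randomized at Visit 4b in a 1:1 ratio across the two treatment arms (40 OTX-DP; 40 PV"), up to about 10 more subjects, 20 imputations, two-sided 0.05, SD 1.0, and differences of 0.87, 1.08 and 1.13 units. The model has an intercept, baseline and treatment, so error df = 80 − 3 = 77. Assumed: missing information of 0 to 20%, as the documents give no rate.

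**The plan's own figure.** SAP Section 5 states "A total of 40 subjects in each treatment arm will provide 97.0%, 99.8%, and 99.9% power". The standard error is √(2/40) = 0.2236. A two-sample t test (78 df) gives 97.0%, 99.75% and 99.9%, with product 96.65% against the stated 96.7%. A normal test gives 97.3%, 99.8% and 99.9%, with product 97.0%. The stated 97.0% and 96.7% match the finite-df test.

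**Formulas.** Let λ be the share of variance due to missing data.
- As written: Rubin df = (20 − 1)/λ².
- With EDF = 77: Barnard-Rubin df = 1/(1/Rubin df + 1/v), where v = (1 − λ) × 77 × 78/80.
- Analytic size = probability that |t| on the Barnard-Rubin df exceeds the critical value used as written.

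| λ | Rubin df | Critical value as written | df with EDF = 77 | Critical value with EDF | Size as written | CI too narrow by |
|---|---|---|---|---|---|---|
| none missing | infinite | 1.960 | 77 | 1.991 | 0.0536 | 1.6% |
| 5% | 7,600 | 1.960 | 71 | 1.994 | 0.0539 | 1.7% |
| 10% | 1,900 | 1.961 | 65 | 1.997 | 0.0541 | 1.8% |
| 20% | 475 | 1.965 | 53 | 2.005 | 0.0546 | 2.0% |

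The first row uses the ordinary ANCOVA df. At N = 90 (87 error df) the size runs from 0.0532 to 0.0541 over the same range.

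**Simulation.** Null trials with N = 80, 20 imputations, normal-model imputation on treatment and baseline, 60,000 trials per cell, Monte Carlo SE 0.0009. The bounded scores lie on 0 to 4 in steps of 0.25.

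| Missing | Normal, as written | Normal, EDF = 77 | Bounded, as written | Bounded, EDF = 77 |
|---|---|---|---|---|
| 0% | 0.0548 | 0.0513 | 0.0544 | 0.0508 |
| 5% | 0.0538 | 0.0495 | 0.0540 | 0.0501 |
| 10% | 0.0517 | 0.0477 | 0.0536 | 0.0498 |
| 20% | 0.0524 | 0.0480 | 0.0531 | 0.0485 |

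The gap between the two methods is about 0.4 percentage points throughout.

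**Visit level.** If one time point is null and the others carry the assumed 1.08 and 1.13, with correlation between 0 and 0.9 (assumed) and complete data, a visit is falsely declared significant in 5.1 to 5.4% of trials as written and 4.7 to 5.0% with finite df. If all three are null the rate as written is at most 2.4%.

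**Other effects.** Power at 0.87 units moves from 97.2% to 97.0%. At SD 1.0 the smallest significant difference moves from 1.960 × 0.2236 = 0.438 to 1.991 × 0.2236 = 0.445 units.

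**The case against.** The strongest reply is that this is immaterial: a few tenths of a percentage point of size, and 0.007 units on a score recorded in half units. The SAP also limits the damage, because "statistical significance at all three post-CAC time points is required for a visit to be deemed statistically significant" and visits are tested in fixed order. That is right about the size, and it is why this should be corrected but is no threat to the trial.

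Second, the printed code is provisional. It is, but leaving detail until the final data permits a correction without committing to one, and a df rule belongs in the plan before unmasking.

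Third, the analytic sizes of 0.0541 and 0.0546 assume that the Barnard-Rubin reference is exact, and simulated size does not rise with missingness. This stands: about 0.054 applies when little is missing, and 0.052 to 0.055 describes the whole range better. It was also argued that EDF = 77 becomes conservative. A smaller run (20,000 trials, normal scores) gave 0.046 at 20% missing; the larger one gives 0.048 to 0.0485, close enough to nominal.

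Fourth, the promise of ANCOVA-based CIs and the power figure do not formally bind the pooled analysis to finite df. That is fair. They show what the plan assumes elsewhere; the departure is from the stated 0.05 level and 95% coverage. Finally, the infinite-df default is a property of the named software, not something the documents state.

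**Conclusion.** The concern holds. As written, the pooled primary test has a size of about 0.054 per time point with little missing data, and its 95% CIs are 1.6 to 2.0% too narrow. The error is always anti-conservative, does not accumulate and leaves power essentially unchanged. It alters a conclusion only if the pooled statistic falls between about 1.96 and 1.99 with little missing data; under the plan's assumed effects that is unlikely. The 77 error df and the direction follow from the documents and the software's default. The missing-data range, score distributions and correlations are assumptions, but the excess is already present with nothing missing.

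**What to change.** - Add EDF = number analysed minus 3 (77 at N = 80, 87 at N = 90) to the LS-means and difference calls. This carries over to the key secondary visits.
- For the repeated-measures model, name the denominator df method in the SAP and pass that df to the pooling call.
- For the t-test sensitivity analysis, EDF= takes one value per call. Use arm size minus 1 for the arm means, and pool the mean difference in its own call with EDF = N minus 2.
- Leave the Wilcoxon pooling as it is, since it uses a normal reference.
- Add one sentence to Section 12.1 stating that Barnard-Rubin small-sample df are used.

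The cost is one option in several calls and one extra call. No new data or subjects are needed. P-values rise slightly and intervals widen slightly.
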